4.5.3. Additional analysis on virologic failure and emergence of resistance

Additional analyses will be conducted to evaluate outcomes within twelve months of initiating RPV or EFV-containing regimens. Specific analyses to be conducted are as follows:

- The proportion of patients with virologic failure within twelve months of RPVcontaining regimens initiation or EFV-containing regimens initiation
- The proportion of patients with treatment emergent RPV or EFV RAMs within 12 months of NNRTI initiation

The decision to prescribe RPV-containing regimens or EFV-containing regimens will be influenced by the treatment recommendations, patient characteristics, the prescriber assessment of the health status and risk profile, and the local policies and formularies. Thus, when planning to compare rates of virologic failure and emergence of resistance, it will be important to first determine whether the populations are comparable. The parameters available in the HIV cohorts will be used to investigate the relative importance of patient characteristics or risk factors that may be used to identify which patients are selected to receive RPV-containing regimens compared with EFV-containing regimens.

The evaluation of appropriateness of a comparison of RPV-exposed patients with EFVexposed patients will be based on the consistency of the clinical experience of the two treatment groups. This assessment will be conducted based on distribution of propensity scores for receipt of RPV-containing regimens or EFV-containing regimens.

The evaluation of clinical experience will assess the patients' clinical and demographic characteristics in relation to receipt of RPV or EFV-containing regimens. Information will be captured on the patients' clinical and demographic characteristics that could be predictive of RPV treatment appropriateness. This information will be incorporated into multivariate models to identify a group of patients with similar characteristics to the RPV-containing regimens cohort but treated with EFV-containing regimens. All patients

will be assigned a propensity score ranging from 0 to 1 that represents the fitted probability of receiving RPV-containing regimens. The scores from EFV-treated patients will be plotted against those for RPV-treated patients. Overlap in the treatment groups based on sample size estimates of approximately 600 patients per treatment group in the propensity space must exist for a comparison of outcomes of interest between the two groups.

Incidence rates of virologic failure, pre-treatment resistance, and treatment-emergent resistance will be calculated for the RPV and EFV-exposed patients. The three primary event rates of interest (incidence rates of virologic failure, pre-treatment resistance, and treatment-emergent resistance) will be analyzed in 3 separate sets of analyses. Additional descriptive analyses will include incidence rates for each drug calculated by dividing the number of events by the total person-exposure time and expressed as the number of events per person-year, and 95% confidence intervals. Analyses of virologic failure will be stratified by HIV treatment status (naïve/experienced) at treatment initiation.

Relative risks comparing the RPV-containing regimens with EFV-containing regimens and 95% confidence intervals will be calculated and appropriate stratified analyses will be conducted for virologic failure and emergence of treatment resistance. Poisson regression models will be used to adjust for the appropriate factors that influence the risk of virologic failure and treatment-emergent resistance. Adjustments for imbalances between the treatment groups before receiving the first dose of RPV or EFV-containing regimens will be applied using accepted methods based on sample size availability and the observed overlap of key patient characteristics based on propensity score construction.

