The development of resistance and the utilization of RPV-containing products according to the products' SmPC will be assessed through a drug utilization study (DUS) conducted in HIV observational cohorts within Europe. Additionally, the DUS will provide context to the observed rates of virologic failure and development of resistance for patients initiating RPV treatment by describing the treatment outcomes of patients initiating efavirenz (EFV). The relative risk of virologic failure and resistant-associated mutations (RAMs) after initiating RPV-containing regimens will be estimated separately by comparing the incidence rates of virologic failure and RAMs among RPV-treated patients to the incidence of virologic failure and RAMs among EFV-treated patients. For all study objectives, frequency and rates will be reported for the RPV and EFV-treated groups separately, as well as for RPV relative to EFV.

The objectives of the DUS are to describe the following in the context of routine clinical practice:

Primary objectives:

- To describe the proportion of patients treated with RPV in accordance with the SmPC The proportion of patients treated with RPV in accordance with the SmPC will be described by estimating a proportion separately for each recommendation of patient treatment. The denominator for each proportion will consist of the number of all patients initiating RPVcontaining regimens included in the study. Proportions will be estimated separately using the following numerators:
 - o The number of patients naïve to HIV treatment regimens
 - o The number of patients with documented pre-treatment screening for ARV RAMs
 - The number of patients initiating RPV-containing regimens with a baseline viral load \leq 100,000 HIV-1 ribonucleic acid (RNA) copies/mL
- To describe treatment emergent RAMs in patients treated with RPV or EFV-containing regimens
- To describe virologic failure in patients treated with RPV or EFV-containing regimens

Secondary objectives:

- To describe the demographic characteristics, comorbidities, and medical condition of patients initiating RPV or EFV treatment
- To describe antiretroviral (ARV) treatment status (naïve/experienced) of patients prior to initiating RPV or EFV treatment
- To describe prior use of ARV treatment, if any, of patients initiating RPV or EFV-containing regimens
- To describe the frequency of pre-treatment RAMs for RPV and EFV among patients subsequently initiating RPV or EFV treatment respectively

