4.2.2. Outcome Definition and Measures

Outcome definitions for the DUS will include:

- HIV viral load prior to initiating RPV-containing regimens or EFV-containing regimens as well as over the course of therapy
- Virologic failure defined for treatment naïve patient as plasma HIV-1 RNA levels >500 copies/ml after 6 months of regimen initiation if baseline viral load is >500 copies/ml. For patients undetectable at baseline virologic failure is defined as 2 consecutive plasma HIV-1 RNA levels >500 copies/ml after starting the regimen.
- HIV treatment status (naïve/experienced) at RPV or EFV treatment initiation
- Prior use of ARV treatment, if any
- NNRTI drug resistance at RPV or EFV treatment initiation as well as over the course of therapy
- Proportion of patients who have resistance testing prior to initiating RPV or EFV therapy as well as over the course of therapy

- Concomitant medications prior to initiating RPV or EFV therapy as well as over the course of therapy
- Comorbidities prior to initiating RPV or EFV therapy as well as over the course of therapy
- Reason for discontinuation of RPV or EFV-containing products
- Reason for switch of ARV treatment
- Adverse events over the course of RPV or EFV therapy

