4.2.5. Length of Follow-up

Each patient will be followed for 12 months from the initiation of RPV or EFVcontaining regimens, or until death, loss to follow-up within the cohort, or virologic failure, whichever occurs first. Time varying variables will be recorded at each patient visit.

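### The 12-month proportion with virologic failure (and with RAMs) has no stated denominator, and under loss to follow-up neither obvious choice recovers the 12-month risk; report cumulative incidence instead

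*Protocol*

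**What the plan says.** Protocol Section 4.5.3 names this among its additional analyses: "The proportion of patients with virologic failure within twelve months of RPVcontaining regimens initiation or EFV-containing regimens initiation". A second item asks for the corresponding proportion with treatment-emergent RAMs. Neither item gives a denominator or a rule for patients not observed to month 12.

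Section 4.2.5 plans 12 months of follow-up, "or until death, loss to follow-up within the cohort, or virologic failure, whichever occurs first".

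Section 4.2.2 sets two routes to virologic failure. For treatment-naïve patients it is "plasma HIV-1 RNA levels >500 copies/ml after 6 months of regimen initiation if baseline viral load is >500 copies/ml". The other route has no six-month wait: "For patients undetectable at baseline virologic failure is defined as 2 consecutive plasma HIV-1 RNA levels >500 copies/ml after starting the regimen".

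The comparison of the two drugs is set up differently. The Synopsis bases it on "comparing the incidence rates of virologic failure and RAMs among RPV-treated patients to the incidence of virologic failure and RAMs among EFV-treated patients". Section 4.5.3 computes rates by "dividing the number of events by the total person-exposure time and expressed as the number of events per person-year", and adds that "Poisson regression models will be used to adjust for the appropriate factors".

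Section 4.4 leaves missing data open between complete-case analysis and imputation. The all-initiators denominator in Section 4.5.2 is written for the SmPC appropriate-use proportions only.

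**The concern.** A simple proportion within twelve months is well defined only when everyone is observed to failure, to death or to month 12. Here some patients will be lost earlier. Take a treatment-naïve patient with a baseline viral load above 500 copies/ml who is lost at month 4. That patient could not yet have met the failure definition, and the 12-month outcome is unknown. Keeping the patient in the denominator lowers the proportion. Dropping the patient while retaining everyone who failed before being lost raises it.

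Describing virologic failure and treatment-emergent RAMs in each group is a primary objective (Section 1.3.1). The 12-month proportion is therefore a planned summary of a primary outcome, even though it is listed as an additional analysis. A person-year rate does not replace it, because a rate is not a 12-month risk.

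**Working it through.** **The plan's own figures.** The protocol states no expected value or precision for the failure proportion. Its only stated precision for a proportion is ±0.02 for 95% appropriate use with 600 patients (Section 4.1.1). This reproduces: 1.96 × √(0.95 × 0.05 / 600) = 0.0174. The same formula at 90%, and so equally at 10%, gives 0.0240, which serves as a yardstick below.

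**Inputs.** Loss by 12 months, L, is assumed at 5% to 30%, independent of failure, because the protocol gives no rate. The true 12-month risk, R, is set at 10% (assumed) or 29.5%. The latter comes from the EFV rate of 0.35 per person-year in the older cohort cited in Section 1.1: 1 − exp(−0.35) = 0.295.

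**Quick check.** With failures spread evenly over months 6 to 12 and μ = −ln(1 − L), the ratio of the all-initiators proportion to the true risk is the mean of exp(−μt) for t from 0.5 to 1 year:

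(exp(−μ/2) − exp(−μ)) / (0.5μ)

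- L = 10%: (0.9487 − 0.9000) / 0.0527 = 0.924
- L = 20%: (0.8944 − 0.8000) / 0.1116 = 0.846
- L = 30%: (0.8367 − 0.7000) / 0.1783 = 0.766

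**Two hazard models.**

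- Model A, constant failure hazard all year: λ = −ln(1 − R), and all-initiators proportion = λ/(λ+μ) × (1 − exp(−(λ+μ))).
- Model B, failure only in months 6 to 12: λ = −ln(1 − R)/0.5, and all-initiators proportion P = exp(−μ/2) × λ/(λ+μ) × (1 − exp(−(λ+μ)/2)).
- Complete cases under B (failures plus those observed for 12 months): P / (P + exp(−μ)(1 − R)).

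| R | L | All initiators, A | All initiators, B | Complete cases, B |
|---|---|---|---|---|
| 10% | 5% | 9.75% | 9.63% | 10.12% |
| 10% | 10% | 9.50% | 9.25% | 10.24% |
| 10% | 20% | 8.98% | 8.47% | 10.53% |
| 10% | 30% | 8.44% | 7.67% | 10.86% |
| 29.5% | 10% | 28.08% | 27.30% | 30.09% |
| 29.5% | 30% | 25.07% | 22.72% | 31.53% |

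At R = 10% and 30% loss, the model B shortfall is 10.00 − 7.67 = 2.33 percentage points, about the same as the 2.40-point sampling half-width with 600 patients. At 10% loss it is 0.75 points. Under independent loss, a time-to-event estimate returns R in every row.

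**RPV versus EFV, true ratio 1, R = 10%.** The person-time rate divides failures by observed time. Under B, that time is (1 − exp(−μ/2))/μ + exp(−μ/2)(1 − exp(−(λ+μ)/2))/(λ+μ).

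| Loss RPV / EFV | Crude ratio, A | Crude ratio, B | Complete-case ratio, B | Rate ratio, A | Rate ratio, B |
|---|---|---|---|---|---|
| 10% / 10% | 1.00 | 1.00 | 1.00 | 1.00 | 1.00 |
| 5% / 20% | 1.09 | 1.14 | 0.96 | 1.00 | 1.05 |
| 10% / 30% | 1.13 | 1.21 | 0.94 | 1.00 | 1.07 |
| 20% / 10% | 0.95 | 0.92 | 1.03 | 1.00 | 0.97 |

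The small residual in the rate ratio under B arises because months 0 to 6 add person-time in which failure cannot be declared.

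**The case against.** Four objections carry weight.

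- **The protocol does not say that lost patients are non-failures.** A reader might infer it from the all-initiators denominator in Section 4.5.2, but that rule covers appropriate use only. Section 4.4 allows complete-case analysis, which reverses the bias, or imputation. This stands: the direction of the error is not fixed by the text.
- **The drug comparison does not use this proportion.** It rests on person-time rates and Poisson regression, which stop counting time when follow-up ends. This largely stands. A reader might conclude that the RPV versus EFV result is distorted, citing a crude ratio of 1.21. That figure needs 30% loss on EFV against 10% on RPV, and the protocol offers no loss rates. Equal loss gives 1.00, and reversing which group loses more reverses the direction.
- **Deaths are not the problem.** A cumulative incidence with death as a competing event also treats a patient who dies before failing as never failing. With deaths and no loss, it equals crude n/N. This stands, so the point concerns loss to follow-up only.
- **Denominators and censoring rules are often left to a separate SAP, which is not shown.** An unstated denominator alone would not be a finding. But the protocol does name the summary, a plain proportion, and that summary misses the 12-month risk with either obvious denominator.

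In addition, the six-month argument concerns virologic failure only. For RAMs just the general effect of loss applies, and it has not been sized here. Patients undetectable at baseline can fail at any time, so a mixed population lies between models A and B.

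**Conclusion.** The point holds as a limited one. Under loss to follow-up, the plain 12-month proportion does not estimate the 12-month risk of failure. Over all initiators it is too low: by about 8% relative at 10% loss and 23% at 30% if failures occur only in months 6 to 12, and by about 5% and 16% if they are spread over the year (R = 10%). Over complete cases it is slightly too high, 10.2% to 10.9% for a true 10% at the same losses. All of this assumes independent loss at rates the protocol does not give.

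A distortion of the crude contrast between the drugs is conditional on unequal loss. The documents do not support a claim that the planned comparison is materially biased: its rate ratio stays at 1.00 under a constant hazard and moves to between 0.97 and 1.07 in the unequal-loss scenarios of model B.

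**What to change.** In Section 4.5.3, report the 12-month risk of virologic failure and of treatment-emergent RAMs in each group as a cumulative incidence with 95% CI. Censor at loss to follow-up and treat death as a competing event (Aalen-Johansen). Keep crude n/N as a description, with its denominator stated and the number lost before month 6 beside it, by group. For RAMs, the wording should also say how patients whose follow-up ended at virologic failure enter, because Section 4.2.5 stops follow-up there.

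The cost is analysis wording only: the person-time analysis already needs the event and follow-up times. The downside is reliance on independent censoring. If patients who leave a cohort are more likely to fail, cumulative incidence will still be too low; the reported numbers lost let a reader judge how much that could matter.

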Virological response to highly active antiretroviral therapy (HAART) regimens has been evaluated among patients enrolled in large, observational HIV cohorts. These studies have included evaluations of NNRTI and protease inhibitor (PI)-containing regimens (Paredes, 2000; Cozzi-Lepri, 2002) as well as short term and long term virological response when treated with NNRTI or PI-based HAART regimens (Mocroft, 2006). A few cohort studies have specifically examined virological failure among patients initiating nevirapine (NVP)-containing regimens or EFV-containing regimens. Phillips and colleagues conducted a study among 2203 patients in EuroSIDA who began a regimen with nevirapine or efavirenz after July 1997 (Phillips, 2001). A total of 1325 patients initiated NVP and 878 EFV. During a median of 8 months follow-up, 669 patients experienced virological failure giving an overall rate of 0.48 per year (0.83 per year if excluding those in first 6 months of follow-up who had baseline viral load >500

copies/ml). A total of 505 people on a NVP regimen experienced virological failure compared with 164 people on an EFV regimen, giving incidence rates of 0.55 per personyear and 0.35, respectively. A more recent EuroSIDA analysis examined virological outcome and drug resistance in 759 patients starting NNRTI-containing regimens (Bannister, 2008). A total of 287 (78.3%) of the 389 NVP patients and 168 (45.4%) of the 370 EFV patients experienced virological failure. NNRTI-resistant HIV was detected in 3% of patients at baseline. Out of the 131 patients still on an NNRTI and with resistance test results available at time of virological failure, NNRTI resistance was detected in 86% of patients and was similar between groups. The high levels of NNRTI resistance suggest that these drugs fostered selection pressure, and that patients had actually adhered to their regimens.

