1.3. STUDY OBJECTIVES

1.3.1. Primary Objectives:

The primary objectives were specifically chosen to meet the CHMP request to assess appropriate use of RPV-containing products. For all primary objectives, frequency and rates will be reported separately for the RPV and EFV-treated groups.

- To describe the proportion of patients treated with RPV-containing products in accordance with the SmPC. The proportion of patients treated with RPV in accordance with the SmPC will be described by estimating a proportion separately for each recommendation of patient treatment. The denominator for each proportion will consist of the number of all patients initiating RPV-containing regimens included in the study. Proportions will be estimated separately using the following numerators:
 - The number of patients naïve to HIV treatment regimens
 - The number of patients with documented pre-treatment screening for ARV RAMs
 - \circ The number of patients initiating RPV-containing regimens with a baseline viral load \leq 100,000 HIV-1 ribonucleic acid (RNA) copies/mL
- To describe treatment emergent RAMs in patients treated with RPV or EFVcontaining regimens
- To describe virologic failure in patients treated with RPV or EFV-containing regimens

The primary objective of the nested case-control analysis is to quantify separately the risk of virologic failure associated with ARV treatment adherence and pill intake with food.

1.3.2. Secondary Objectives:

The secondary objectives were specifically chosen to assist in meeting the CHMP request to assess appropriate treatment of patients with RPV-containing products in accordance with the SmPC or to provide context to events observed within the RPV-treatment group. For all secondary objectives, frequency and rates will be reported separately for the RPV and EFV-treated groups, as well as for RPV relative to EFV.

• To describe the demographic characteristics, comorbidities, and medical condition of patients initiating RPV or EFV treatment

- To describe antiretroviral (ARV) treatment status (naïve/experienced) of patients prior to initiating RPV or EFV treatment
- To describe prior use of ARV treatment, if any, of patients initiating RPV or EFV-containing regimens
- To describe the frequency of pre-treatment RAMs for RPV and EFV among patients subsequently initiating RPV or EFV treatment respectively
- To describe viral load at start of RPV or EFV treatment
- To describe viral load over the course of RPV or EFV treatment

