Exposure to RPV will be determined by the presence of prescription records for the FDC of FTC/RPV/TDF or single agent of RPV among patient data. Relevant drug codes will be used to identify RPV-containing regimens in the HIV cohorts. The baseline date for exposure follow-up (index date) for a patient within a given treatment group will be defined by first prescription of RPV or EFV-containing regimens. Duration of exposure will be based on dispense date and days of supply for each dispensed prescription. Exposure to RPV or EFV-containing regimens will be considered discontinued if the prescription is not refilled within a specified interval of time (e.g. twice the days' supply) of the previous prescription. Switches from one drug to another will be captured and time on drug will be defined by the exposure periods. The total length of exposure to a given drug will be the time between start and stop periods of exposure to the same drug.

4.2.1.1. **Exposure Definition in Nested Case-Control Study**

For the nested case-control analysis, exposure will be based on 1) level of daily medication adherence, and 2) level of adherence to food recommendations. Cases and matched controls that are selected will be asked to retrospectively report via a questionnaire how often they took their HIV medication during a specified time period and how often RPV was taken with food. A single item querying the number of prescribed doses the participant had missed in a specified time period will be used, as follows:

"How many doses of your complete HIV regimen did you miss in the last 7 days?"

"For those days you missed, what component of your HIV regimen did you miss?" (If applicable)

"How often did you take RPV with food in the last 7 days?"

Since RPV dosing is once-daily, number of doses taken is equivalent to number of days the medication is taken. A 7-day recall period is proposed for this analysis as it has the advantage of including a weekend, during which adherence is often problematic. Further, DATE (6 September 2011) 20

longer recall periods (7-day vs. 1-3 day) may yield more useful data for once-daily ART dosing since there are too few dosing times in a very brief recall period to capture variations in adherence behaviors (Simoni, 2006).

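### Pre-treatment resistance is listed as a primary incidence rate per person-year of exposure, though it is a baseline prevalence; and no rule says whether genotypes drawn after virologic failure count as emergent

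*Protocol*

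**What the plan says.** **Pre-treatment resistance.** Section 4.5.3 states: "Incidence rates of virologic failure, pre-treatment resistance, and treatment-emergent resistance will be calculated for the RPV and EFV-exposed patients". It calls these "The three primary event rates of interest (incidence rates of virologic failure, pre-treatment resistance, and treatment-emergent resistance"), to be analysed in separate sets. The rates for each drug are then "calculated by dividing the number of events by the total person-exposure time and expressed as the number of events per person-year". The Synopsis carries the same text. Under section 4.2.1 the index date "will be defined by first prescription of RPV or EFV-containing regimens".

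Section 1.3.2 lists the same quantity as a secondary objective, and as a frequency: "To describe the frequency of pre-treatment RAMs for RPV and EFV among patients subsequently initiating RPV or EFV treatment respectively". That section wants frequencies and rates for all secondary objectives, by group and for RPV relative to EFV. Sections 4.3.1 and 4.3.2 add rates of baseline resistance by group and a comparison between the groups.

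**Emergent resistance.** Describing treatment-emergent RAMs is a primary objective (section 1.3.1). Section 4.5.3 asks for "The proportion of patients with treatment emergent RPV or EFV RAMs within 12 months of NNRTI initiation". Section 4.2.5 follows each patient for 12 months "or until death, loss to follow-up within the cohort, or virologic failure, whichever occurs first". The Synopsis and sections 3.1 and 7.2.1 also end follow-up at failure. Section 4.2.2 measures resistance at initiation and during therapy and gives no window around failure.

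**The concern.** An incidence rate counts new events among people at risk, over the time in which the events could occur. Resistance already present at the first prescription cannot arise during later exposure. Dividing it by that exposure gives a number that falls when patients stay on the drug longer and rises when they stop or fail early. An RPV-EFV ratio of such numbers would partly measure persistence and failure, which are outcomes of treatment.

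The rank also matters. One section makes this a primary event rate and another a secondary objective, so the report could headline it either way.

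For emergent RAMs, the protocol's own background cites resistance found at failure: "Out of the 131 patients still on an NNRTI and with resistance test results available at time of virological failure". If follow-up closes on the failure date, a genotype from a later sample has no stated place in the analysis. Resistance is one of the two matters on which the CHMP asked for further assessment, so both figures should be defined without ambiguity.

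**Working it through.** The protocol gives no expected rate, precision or power for resistance, so there is no planned figure to reproduce. One background input can be checked. In the cohort of 2,203 patients in section 1.1, person-years are 164/0.35 + 505/0.55 = 468.6 + 918.2 = 1,386.8, and 669/1,386.8 = 0.48 per year, as printed.

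**1. Pre-treatment resistance per person-year.** With prevalence *p* and mean exposure *m* years, the section 4.5.3 formula gives *Np*/(*Nm*) = *p*/*m*. If *p* is equal in the two groups, the RPV/EFV ratio is *m*(EFV)/*m*(RPV), which contains no information on resistance.

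Inputs: *p* = 3%, the baseline NNRTI resistance in the section 1.1 background, used only as illustration. Mean exposures are assumed; the protocol gives none.

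| Mean exposure RPV, EFV (years) | Rate per 100 person-years | Ratio |
|---|---|---|
| 0.95, 0.90 | 3.2, 3.3 | 0.95 |
| 0.95, 0.75 | 3.2, 4.0 | 0.79 |

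A second illustration lets follow-up end at failure or 12 months, with a constant failure rate *r*, so *m* = (1 − e^(−r))/*r*. With the background failure rates and 600 patients per group (600 × 0.03 = 18 with resistance):

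- *r* = 0.35: *m* = 0.844, 506 person-years, 18/506 = 3.6 per 100 person-years.
- *r* = 0.55: *m* = 0.769, 461 person-years, 18/461 = 3.9 per 100 person-years.
- Ratio of the second to the first: 0.844/0.769 = 1.10.

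As a prevalence, every row and both groups give 18/600 = 3.0%.

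**2. Emergent RAMs.** Assume *r* = 0.35, all failures genotyped, and 86% of them with RAMs (the background figure among patients still on an NNRTI with a result at failure). Failures: 600 × (1 − e^(−0.35)) = 177. With RAMs: 0.86 × 177 = 152. The 12-month proportion then depends on the share of these genotypes that come from samples dated after failure and are left out:

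| Share left out | 12-month proportion |
|---|---|
| 0% | 152/600 = 25.4% |
| 25% | 19.0% |
| 50% | 12.7% |
| 100% | 0% |

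The first row applies if all genotypes come from the failing sample. The last is a bound, not an expectation. The protocol does not say when genotypes are drawn, so the position between these rows is unknown. The background rates come from earlier NVP and EFV cohorts and are not forecasts for this study.

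**The case against.** **On pre-treatment resistance.** Section 1.3.2 already plans a frequency among initiators, so a correct summary survives. The person-year formula is introduced as an additional descriptive analysis and does not name pre-treatment resistance. No section specifies an RPV-EFV ratio of person-year rates for it. All of this is true, and it limits the harm. But section 4.5.3 lists the quantity among the incidence rates, defines such rates without exception, and sections 1.3.2 and 4.3.2 call for a comparison between drugs. Followed as written, this yields an invalid figure beside a valid one, with conflicting rank.

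A reader might infer that the Poisson models are affected too. They are not: section 4.5.3 limits relative risks and Poisson regression to virologic failure and emergent resistance.

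**On emergent resistance.** A reader might infer that this figure is wrong as well. The protocol does not support that. Time on drug is a legitimate base for emergent resistance, and a genotype from the sample that defines failure falls inside follow-up. If those samples supply the results, nothing is lost.

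A reader might also set the 131 patients in the background against that cohort's 287 + 168 = 455 failures, take 29% as a testing rate, and conclude that RAMs will be undercounted several-fold. But the 131 were both still on an NNRTI and tested, so the fraction mixes stopping the drug with not being tested. Nor does any section say that untested patients count as free of RAMs. Section 4.4 leaves complete-case analysis or imputation open, and section 4.2.2 already reports the proportion tested during therapy. The operational definition of emergent can be left to the statistical analysis plan.

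**Conclusion.** The pre-treatment part holds. The listed rate is not an incidence, and with equal prevalence its ratio between drugs is the inverse ratio of mean exposure: 0.95 to 0.79 under the assumed exposures, and 1.10 under the background failure rates. The size depends entirely on how far exposure differs between the groups, which is unknown; with equal exposure the ratio is 1. The primary/secondary conflict stands whatever the numbers.

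For emergent RAMs the finding is narrower: an unstated rule for genotypes drawn after the failing sample, which sits badly with a 12-month proportion counted from initiation. Any bias is downward if such samples are left out, and nil if the failing sample supplies the genotype. The figure is possibly understated, not shown to be wrong.

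**What to change.** 1. In section 4.5.3 and the Synopsis, delete pre-treatment resistance from the list of incidence rates.
2. Report it by drug as a proportion with 95% CI among initiators with a pre-treatment genotype, with the number tested. Make any RPV-EFV comparison under sections 1.3.2 and 4.3.2 on proportions, and have section 4.3.1 say the same.
3. Give it one rank, primary or secondary, in sections 1.3 and 4.5.3.
4. In section 4.2.5 or 4.5.3, state that genotypes from the failing sample, and from later samples within a stated window, count toward emergent RAMs. Say how that window relates to the 12-month horizon. Its length is for the sponsor to choose.
5. Report the number and proportion of failures genotyped, by drug, beside the emergent figure.

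The cost is wording and a little more reporting. Section 2.2 says the cohorts follow patients until death or loss to follow-up, so later genotypes may already be held, but the detail of the resistance data is still under feasibility assessment. The denominator for pre-treatment resistance shrinks. At 3%, the approximate 95% half-width is 1.96 × √(0.03 × 0.97/600) = 1.4 percentage points with 600 tested, and 1.7 points if only 400 were tested (assumed).
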